Data from randomized clinical trials and observational studies suggest relapse is common if rituximab is discontinued indefinitely. Among patients in the RAVE trial who achieved complete remission following treatment with rituximab, 32% had a relapse within 18 months(9).

Furthermore, Alberici *et al* reported that 41% of patients who received maintenance rituximab every 6 months for 24 months relapsed at a median of 34.4 months following discontinuation of therapy(17). Predictors of relapse included return of B cells and change from ANCA negativity to positivity(17).

Survival of ANCA vasculitis patients undergoing rituximab-induced continuous B cell depletion

A prospective and longitudinal clinical trial is needed to determine the ideal treatment strategy for long-term maintenance of remission. Here we propose to compare 2 strategies once patients have

been in sustained remission on scheduled rituximab dosing with a goal of undetectable B cells for greater than or equal to 2 years. Target enrollment is 200 subjects over 48 months from the time the first patient is enrolled to be followed for a common close out date of 36 months after the last subject is enrolled.

The study design is an open-label, single center, randomized and two-arm controlled trial to evaluate the optimal maintenance of remission strategy that provides the best relapse-free survival in patients with ANCA vasculitis as determined by relapse-free remission at 18, 24 and 36 months from enrollment. Subjects with ANCA vasculitis in sustained remission on regularly scheduled rituximab infusions with a goal of undetectable B cells for a minimum of two years who meet specific entry criteria will be randomized with stratification based on ANCA subtype and rituximab vintage (i.e., duration of continuous rituximab prior to enrollment) to one of two arms :

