When a potential subject is identified, the research nurse will initially explain the study to the patient after their clinical visit with [name], [name], or [name]. If the patient expresses further interest in participating in the study, [name], [name], or [name] and the research nurse will then review the study details with the patient. The patient will be provided the opportunity to take the consent form home to further review and will follow-up with the research nurse or investigator within 14 days. If they decline participation, they will continue to receive their standard of care as deemed appropriate by their treating clinician. Massachusetts General Hospital is expecting to enroll up to 200 subjects over 36 months.

C. Treatment assignment and randomization

Each subject will be stratified prior to randomization to ensure MPO- and PR3-ANCA serotypes and duration of rituximab therapy are approximately equal within each arm. Randomization will occur using random permuted blocks to assign each subject to one of two arms:

1. Treatment upon B cell return, OR
2. Treatment upon a significant rise in ANCA titer as defined above.

V. Study Procedures

A. Study visits and parameters to be measured

1. Potential subjects will be identified during a clinical visit. Medical records will be reviewed by study staff and if found eligible then the potential subjects will be offered the opportunity to participate in the study at that visit. Potential subjects will have 14 days to decide on participation.
2. "Day 0" is defined as the date of the last rituximab infusion prior to randomization and must be 6 months +/- 14 days from Study visit 1. Existing data will be collected from this date once enrolled and randomized.
3. **Study Visit 1: Enrollment and Randomization**
 - a. Patients who agree to participate and have signed and dated the consent form will be randomly assigned to one of two treatment arms:

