 5. ESR
 6. CRP
 7. Hep B sAg, Hep C Ab, HIV ½ (if not performed in the previous 12 months prior to screening and only at enrollment)
 8. Immunoglobulin levels
 9. Flow cytometric analysis of peripheral B and T cells
 10. Urinalysis
 11. Urine human chorionic gonadotropin (hCG) in women of child bearing potential
 - xi. Quality of life surveys SF36 v2 and EQ 5D-5L
 - xii. Baseline ECG
 - xiii. Cough assessment/scale
4. Study Visits 2-16: Study visit 2 will occur at the 6 month time point from Day "0" (+/- 14 days) and subsequent visits will take place every three months (+/- 14 days) thereafter until a common close out date of 36 months after the last subject is enrolled.
 - a. Subjects will be seen every three months in clinic and the same measurements will be performed as listed in the Enrollment and Randomization Visit.
 - i. The VDI Score will only be calculated every other visit after Study visit 2 as this score is designed to measure cumulative damage every six months.
 - ii. Subject quality of life assessments SF 36v2 and EQ-5D-5L will be assessed every 6 months from time of Study visit 2.

- iii. ECG will be performed every 12 mos
- iv. Adverse Events will be assessed at each visit
- v. Cough assessment/scale
- b. In cases where subjects need to come in for an infusion in between scheduled visits, the visit directly after the infusion may be done over the phone instead of coming in to the clinic. This will be decided at the discretion of the PI based on any hardships the patients may have related to distance of travel. The same measurements will be performed as an on-site visit (VDI score, BVAS, adverse events, and cough/assessment), except for the ECG and blood draw. The ECG will be added to the next office visit, and blood work will be deferred for that visit, and resumed at the next time point. Subject Quality of Life Assessments SF36v2 and EQ-5D-5L may be mailed to subjects for completion, then returned at the next office visit.
- c. If subjects miss their scheduled visits and are unable to reschedule in window, a deviation will be filed and an investigator will call them to assess AEs and disease activity.
- d. Subject visits can be completed as telemedicine with remote lab draws during the COVID-19 pandemic. Lab draws may be delayed up to 4 weeks at the investigator's discretion. A minor deviation will be filed if lab draws occur outside that window.

B. Drugs to be used

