Data will be analyzed by the intention-to-treat principle. Randomization will be stratified on ANCA subtype (MPO vs PR3) and rituximab vintage (< 3 years vs > 3 years). Rituximab vintage is the duration of continuous rituximab therapy administered prior to enrollment in the study. We have contracted with the company StudyTRAX to perform randomization on stratified variables via random permuted blocks.

Continuous data will be summarized using descriptive statistics. Continuous data will be assessed using the t-test or Wilcoxon rank-sum test as appropriate. Categorical data will be assessed using the Chi-square and the Fisher exact tests as appropriate. The probability of remaining free of relapse will be estimated using the Kaplan-Meier method. The difference between the two

treatment strategies will be assessed using the log-rank test. *P* values of 0.05 will be considered significant.

D. Power analysis

Using a two-sided logrank test with an alpha level of 0.05, a projected relapse risk of 15% in the superior group and 30% in the inferior group, and an estimated enrollment time of 36 months, it was determined that 180 patients are required to detect a significant difference with a power of 0.80. We aim to enroll 200 patients in the study.

VII. Risks and Discomforts

Subjects may experience side effects while receiving rituximab, which is given as part of their regular medical care for their GPA or MPA. As per the entry criteria, subjects have been on rituximab for 2 years prior to enrollment, the side effects have been discussed in detail and a signed consent for rituximab is obtained for every patient receiving rituximab at the first dose and annually thereafter.

The effects of rituximab on a fetus are unknown and may be harmful. Individuals of childbearing potential should use effective birth control during treatment and for 12 months after their last rituximab infusion. Prior to any infusion of rituximab to a woman of childbearing potential, a urine pregnancy test is performed and recorded. If a woman is found to be pregnant, she will then be removed from the study and followed based on best medical judgment as deemed appropriate by the clinician investigator.

A. Complications of surgical and non-surgical procedures

Not applicable

B. Drug side effects and toxicities

Common side effects of Rituxan

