
E. Psychosocial (non-medical) risks

There are no known psychosocial risks associated with this study, however there may be unknown risks that will be addressed if they become known.

F. Radiations Risks

Not applicable

VIII. Potential Benefits

A. Potential benefits to participating individuals

There may not be any direct benefits to subjects who participate in this trial. Information learned by conducting this trial may benefit future patients by helping determine a long term plan with regards to rituximab administration for patients with GPA or MPA.

B. Potential benefits to society

This study, once completed, will be a landmark trial in the field of remission maintenance therapy for ANCA vasculitis. Currently, specialists do not know the ideal treatment strategy for this subset of patients and this study is likely to provide the answer. In addition, if it is found that either Arm 1 or Arm 2 are as effective as ongoing continuous therapy, there will be cost-effective benefit to society in that less rituximab will be required to maintain remission.

IX. Monitoring Quality and Assurance

A. Independent monitoring of source data

The PI on this study will be responsible for the data management, integrity of this data and adherence to the IRB-approved protocol. The PI will review the accuracy and completeness of entries, source documents, and informed consent on a regular basis.

Privacy of subjects will be protected and confidentiality of data collected maintained. All individually identifiable information will be stored in a secure, locked, location in the PI's office. Password-protected computer databases will be used with limited access to the study data. Files for data analysis will contain codes instead of identifiers. All identifiers will be removed once study is completed.

B. Safety monitoring

The patient's treating physician will be responsible for the treatment of any adverse events, in accordance with the approved product labeling and the physician's discretion.

Subjects will be withdrawn from the study at any point for the following reasons:

1. Serum IgG < 250 mg/dL at any point during the study.
2. Modified BVAS-WG ≥ 2
3. Require daily prednisone >7.5mg

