4. WBC <3,000
5. Serious Infections that require hospitalization.

The investigators will also review the data every 6 months to ensure there are no safety concerns or clear inferiority in one arm that would warrant early termination of the trial.

C. Outcomes monitoring

The following outcomes will be collected throughout the study period as appropriate:

1. Disease flare defined as a BVAS/WG ≥ 2 (**primary aim**). A subgroup analysis will be performed by ANCA subtype.
2. Proportion of patients with serious adverse events (SAEs), including all episodes of LON.
3. Number of infections (mild and severe).
4. Total rituximab utilization during the study period.

5. Patient quality of life assessment using the SF-36v2 and EQ-5D-5L surveys every 6 months
6. Number of major (modified BVAS-WG ≥ 3) relapses
7. Survival
8. Hypogammaglobulinemia (IgG < 400 mg/dL)

D. Adverse event reporting guidelines

All adverse events will be reported per PHRC guidelines which includes unanticipated problems involving risks to subjects/others, including adverse events, within 5 working days/7 calendar days of the date that the investigator first became aware of the problem.

References

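### Withdrawal from the study at five triggers, one of them the primary endpoint, conflicts with follow-up to a common close-out and leaves most secondary outcomes with no planned data source afterwards

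*Combined protocol and SAP*

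**What the plan says.** Section IX.B (Safety monitoring): "Subjects will be withdrawn from the study at any point for the following reasons". The list is serum IgG below 250 mg/dL, modified BVAS-WG of 2 or more, a need for daily prednisone above 7.5 mg, WBC below 3,000, and "Serious Infections that require hospitalization". The second item is also the primary endpoint event of section VI.B. Section VII (Risks and Discomforts) adds: "If a woman is found to be pregnant, she will then be removed from the study".

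Follow-up is described without these exceptions. In section I, subjects are "to be followed for a common close out date of 36 months after the last subject is enrolled". In section V.A, item 4, three-monthly visits run "until a common close out date of 36 months after the last subject is enrolled". Section IX.C, directly after the withdrawal list, says "The following outcomes will be collected throughout the study period as appropriate".

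Section VI.B lists nine secondary endpoints. Section VI.C promises intention-to-treat analysis, Kaplan-Meier and log-rank for relapse, t-test or Wilcoxon for continuous data, and chi-square or Fisher for categorical data. It has no censoring rule, no missing-data rule and no adjustment for exposure.

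**The concern.** The withdrawal is from the study, not only from the assigned dosing strategy. Taken literally, a subject's data end at a trigger, and the most foreseeable trigger is the event that the trial is designed to compare. If flares are more frequent in one arm, that arm tends to be watched for less time, yet the secondary comparisons treat counts, totals and proportions as if observation were equal.

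At stake are Secondary Aim 1 (SAEs), Secondary Aim 3 (rituximab use, where doses given to treat a relapse would be missed), and the comparisons of VDI, quality of life, infections, major relapses, hypogammaglobulinemia and survival. Section VII.C itself warns that relapse can cause irreversible organ damage, so damage and survival data would stop just when they become informative.

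**Working it through.** **1. What follows a trigger.** Section I says that a flaring subject has reached the primary endpoint and is treated at the investigator's discretion; it does not mention observation. The telephone call in section V.A, item 4c, is for missed visits. Follow-up after pregnancy is left to clinical judgment. Section IX.C sets out no visit, call or record review for withdrawn subjects.

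**2. Which outcomes are affected.**
- Not harmed by withdrawal at flare: time to first flare, and the flare-or-SAE composite if analysed as a first event.
- Already counted: an SAE that itself triggers withdrawal.
- IgG below 400 mg/dL: safe for the IgG 250 trigger, since 400 is crossed at or before 250, but cut short by flare, WBC or infection withdrawal.
- Major relapses (BVAS-WG of 3 or more): at most one per subject, and none if the first flare scores exactly 2.
- All infections: counting stops at the first one that needs hospital admission.
- Later SAEs, rituximab use, VDI, quality of life and survival: no planned source.

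**3. The plan's own sample size.** Inputs from section VI.D: 15% and 30% relapse, two-sided alpha 0.05, power 0.80, 36 months of accrual, N = 180. Assumed: 1:1 allocation, exponential relapse, risks read at 36 months, and follow-up t uniform on 36 to 72 months (mean 54).
- Monthly hazards: λ1 = −ln(0.85)/36 = 0.004514; λ2 = −ln(0.70)/36 = 0.009908; HR = 0.456.
- Freedman events: (1.960 + 0.842)² × [(1 + 0.456)/(1 − 0.456)]² ≈ 56.1, so 57.
- Flare by close-out, mean[1 − exp(−λt)]: 0.2155 and 0.4112, average 0.313.
- N = 57/0.313 = 182, against the stated 180.

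The figure reproduces with full follow-up and no loss from non-flare triggers. This does not settle the risk horizon, which the plan does not state: 24-month risks with 36 months of accrual and 18 of minimum follow-up give 184. Section I names 18, 24 and 36 months, so all three are shown below.

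**4. Observation lost when only flares end it.** Months lost per subject = mean[t − (1 − exp(−λt))/λ], divided by 54. SAE proportion observed, with the same true SAE hazard s = 0.10/12 per month in both arms and unrelated to flare (assumed; the documents give no SAE rate) = mean[s/(s + λ) × (1 − exp(−(s + λ)t))]. With full follow-up it would be 36.0% in both arms.

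| Risks read at | Time lost, superior / inferior arm | Observed SAE, superior / inferior arm | False gap (points) |
|---|---|---|---|
| 36 months | 11.6% / 23.1% | 32.2% / 28.3% | 3.9 |
| 24 months | 16.7% / 31.9% | 30.5% / 25.4% | 5.1 |
| 18 months | 21.4% / 39.3% | 28.9% / 22.8% | 6.0 |

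Gaps are taken before rounding. In the 36-month case the losses are 6.27 and 12.49 months per subject, or 52.2 and 104.1 patient-years per 100. The standard error of the difference at 100 per arm is sqrt(0.322 × 0.678/100 + 0.283 × 0.717/100) = 6.5 points.

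A shorter reading is possible. The schedule is headed "Study Visits 2-16: Study visit 2 will occur at the 6 month time point from Day" 0, and Day 0 "must be 6 months +/- 14 days from Study visit 1". Visit 16 then falls at month 6 + 3 × 14 = 48 from Day 0, which is 42 months after enrolment. With 42 months for everyone and 36-month risks, the loss is 8.9% against 18.2% and the gap 2.6 points.

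**5. Why the direction is open** (36-month case). Add an assumed non-flare withdrawal hazard w/12 to s + λ.
- 5% per year in the superior arm and 0% in the inferior: 29.1% against 28.3%, so the gap nearly closes.
- 10% against 2%: 26.5% against 27.3%, so it reverses.
- Time lost is equal when w is higher in the superior arm by 12 × (0.009908 − 0.004514) = 6.5% per year.
- Secondary Aim 1 includes SAEs related to vasculitis activity. If 23.7% of first flares are SAEs, both arms show 36.3%, although the true figures are 39.2% and 42.1%.

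**6. Primary endpoint.** At N = 200, Freedman power = Φ(√E × (1 − HR)/(1 + HR) − 1.96). With non-flare withdrawal of 0, 5 and 10% per year (assumed, equal in both arms, non-informative), expected relapses E are 62.7, 56.4 and 51.1, and power is 0.84, 0.80 and 0.76.

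**The case against.** The strongest reply is that a general visit schedule with listed exceptions is not a contradiction, and that the qualifier closing the lead sentence of section IX.C may mean that collection continues. The first part stands as far as it goes: this is a conflict to reconcile, not proof that the plan is incoherent. The second does not close the gap, because the qualifier can equally mean collection only while the subject is in the study, and no procedure is given. The consent form was not available to check. Even if it covers the point, the protocol should state it.

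It can also be said that the centre treats these patients and will hold their records. That is likely, but nothing plans to use them. Rituximab use up to flare is a coherent target for Secondary Aim 3; the plan simply does not say that this is the target.

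The SAE and withdrawal rates above are assumptions, and the false gap is below one standard error in each case shown. That stands, and it limits the claim to possible bias.

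A reader might infer three stronger things. The first is that the primary comparison is biased. Flare withdrawal cannot do this, since the subject already has the event. Non-flare withdrawals could censor informatively, but the documents do not show that they do, and a subject who needs more prednisone for active vasculitis may already be scored as a flare. The second is that the arm with more flares will necessarily look safer; step 5 shows otherwise. The third is that intention-to-treat analysis is impossible. Subjects can still be analysed in their assigned arm, but with incomplete outcomes.

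**Conclusion.** The concern holds for the secondary outcomes and should be fixed. Sections VII and IX.B end study participation at events that sections I, V.A and IX.C do not treat as the end of follow-up, and the supplied text plans no data afterwards. The secondary comparisons named above can be biased when flare or trigger rates differ by arm, because the planned tests ignore unequal observation.

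The sizes are illustrations. They rest on exponential relapse, 36 to 72 months of follow-up, an unstated horizon for the 15% and 30%, and an assumed SAE rate. Within those limits, flare withdrawal alone costs the inferior arm about twice the share of patient-time that it costs the superior arm. The net direction and size of any bias cannot be read from the documents. The primary endpoint is largely untouched: at N = 200, power is still 0.80 with non-flare withdrawal of 5% per year.

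**What to change.** Leave the clinical criteria and treatment decisions as they are. Reconcile sections VII and IX.B with sections I, V.A and IX.C by stating separately when the assigned strategy ends and when observation ends. Then:

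- Collect BVAS/WG, SAEs, infections, IgG, VDI, SF-36v2 and EQ-5D-5L, all rituximab given and vital status on every randomised subject to the common close-out unless consent is withdrawn. Routine clinic visits, telephone contact or the centre's records would serve.
- Keep subjects who meet a non-flare criterion at risk for the primary endpoint, with a sensitivity analysis that censors at the trigger.
- Report the main secondary outcomes also up to the trigger, and report triggers by arm and reason.

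The cost is an amendment and extra data collection: 52.2 + 104.1 = about 156 patient-years in the 36-month case, or roughly 625 visits if the full three-monthly schedule were kept. It would be more if the risks apply at 18 or 24 months. Most of this falls on patients already seen at the centre, and records or calls would reduce it. Outcomes after a trigger will also reflect physician-chosen treatment, so the full-follow-up comparison is of strategies as assigned; the up-to-trigger reports show how much that matters.

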- 2. Hold continuous dosing with rituximab with re-dosing upon significant ANCA titer increase:** Subjects will no longer receive regularly scheduled every six-month doses of rituximab, and will instead be seen in clinic with the ANCA titer monitoring every three months (beginning 6 months after their last rituximab dose). For MPO, a significant increase will be defined as a 5-fold rise in ANCA titer and a level greater than 4 times the cutoff value for the assay. For PR3, a significant rise will be defined as a 4-fold rise in ANCA titer to a level at least twofold above the cutoff value for the assay. Patients who sustain a significant increase in ANCA titer will receive rituximab 1000mg IV x 2 doses (~2-3 weeks apart). If the ANCA titer then falls to less than twofold above baseline or falls below the specified threshold (the cutoff value of the assay for PR3 and 4 times the cutoff value for MPO) after rituximab, patients will be seen in clinic every three months, with monitoring of ANCA titers. However, if the ANCA titer remains twofold above baseline and above the specified threshold (the cutoff value of the assay for PR3 and 4 times the cutoff value for MPO) after rituximab, patients will continue to receive rituximab 1000mg IV every 6 months for a maximum of 2 doses, at which time a new baseline ANCA titer will be established. Once the new baseline ANCA titer is established, the patients will continue to be seen in clinic every 3 months, with monitoring of ANCA titers. Patients will continue to be dosed with rituximab each time they meet criteria for a significant ANCA titer rise. In this arm, rituximab administration is not contingent upon B cell levels. Rituximab will only be dosed based on the ANCA titer as described above. Baseline ANCA titer will be recalculated to an average of the two highest of the last four values if all four are less than the original baseline. Patients in

the ANCA arm will move to once yearly CD20 testing after CD20 levels return to normal levels (>90 cells/uL).

Patients can be treated at any time during the study period with a total prednisone dose of ≤ 7.5 mg. Patients with a disease flare (defined by BVAS/WG ≥ 2) will have reached the primary endpoint and will be treated for relapse at the discretion of the investigator

II. Specific Aims

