- 1. Primary Aim: To determine whether a rituximab-dosing protocol based on: 1) reconstitution of peripheral B cells or 2) a serologic ANCA flare is more efficacious in preventing relapse in patients with ANCA vasculitis.** Eligible patients will have completed a minimum of 2 years of rituximab maintenance therapy without relapse. The endpoint will be disease relapse defined as a BVAS/WG ≥ 2 . Analysis will also be stratified based on ANCA subtype (due to differences in relapse between patients with MPO and PR3 ANCA) and rituximab vintage.
- 2. Secondary Aim 1: To determine whether a rituximab-dosing protocol based on: 1) reconstitution of peripheral B cells or 2) a serologic ANCA flare is associated with more serious adverse events.** Serious adverse events of interest include those related to vasculitis activity and those that develop as a consequence of rituximab therapy. The main rituximab-associated serious adverse events noted in our cohort are infection, late-onset of neutropenia, and infusion reactions(10)
- 3. Secondary Aim 2: To determine whether a rituximab-dosing protocol based on: 1) reconstitution or peripheral B cells or 2) a serologic ANCA flare is associated with a greater composite of disease relapse (BVAS/WG ≥ 2) and serious adverse events.**
- 4. Secondary Aim 3: To determine whether a rituximab-dosing protocol based on: 1) reconstitution of peripheral B cells or 2) a serologic ANCA flare is associated with greater rituximab utilization during the study period.** While effective, rituximab therapy is costly and increases health care expenditures. Evaluation of the relative cost of the 2 dosing-strategies will assist in the application of these dosing-strategies to the broad population of patients with ANCA vasculitis.

III. Subject Selection

Patients with ANCA vasculitis who are seen at MGH will be recruited as subjects and inclusion and exclusion criteria are detailed below.

A. Inclusion and exclusion criteria

Inclusion criteria:

1. All patients must be able and willing to give written informed consent and comply with the requirements of the study protocol.

2. Diagnosis: ANCA vasculitis as defined by a positive MPO- and/or PR3-ANCA test together with clinical features characteristic of ANCA-positive diseases as detailed in the 2012 Chapel Hill Consensus Conference Definitions(18).
3. eGFR \geq 20 cc/min/1.73m²
4. Age: 18-82 years old

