5. Treated with continuous rituximab at regularly scheduled intervals with a goal of undetectable B cells for at least 24 months.
6. In sustained remission (defined by a modified BVAS-WG=0 **AND** a prednisone dose of \leq 7.5mg for at least 12 months).
7. Undetectable (<10mm³) B cells as quantified by the number of CD20+ cells on peripheral blood flow cytometry on day 0.
8. Urine Hcg negative for women of child bearing potential and not planning to become pregnant for at least 12 months from enrollment and at least 12 months after any study related rituximab dose
9. Judged to be otherwise healthy by the Investigator, based on medical history and physical examination (no known active disease process for which life expectancy is less than 36 months)

Exclusion criteria:

1. Secondary Disease: disease suspected to be induced by levamisole-adulterated cocaine
2. All transplanted patients
3. Treatment: additional immunosuppressive agents other than rituximab and/or total daily prednisone dose \geq 7.5 milligrams
4. Hypogammaglobulinemia: IgG level < 300mg/dL
5. Terminal cancer or other primary illness with life expectancy of less than 36 months
6. Active anti-GBM disease and other known autoimmune disease for which the need for additional immunosuppression is likely
7. Pregnancy or breastfeeding

B. Sources of subjects and recruitment methods

Subjects will be recruited from the current pool of patients in the MGH Renal and Rheumatology Units of the Vasculitis and Glomerulonephritis Center.

IV. Subject Enrollment

A. Methods of enrollment

Patients will be prescreened for eligibility by research staff prior to their scheduled rituximab infusion. Potential subjects will be assessed for eligibility utilizing existing data regarding current length of treatment with rituximab, prednisone dose (if any) and most recent Birmingham Vasculitis Activity Score.

At a regularly scheduled clinic visit, study site personnel will assess a patient's eligibility for enrollment, including review of the inclusion and exclusion criteria. Patients meeting all the inclusion criteria and have no exclusionary criteria and receive treatment for their ANCA Associated Vasculitis by physicians in the MGH Renal and Rheumatology Unit's Vasculitis and Glomerulonephritis Center will be offered the opportunity to participate in this study as part of their ongoing treatment.

B. Procedures for obtaining informed consent

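### Patients withdrawn for steroids, low IgG, low WBC or hospitalized infection leave the study without a planned relapse assessment, so the primary log-rank test in effect censors them

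*Combined protocol and SAP*

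**What the plan says.** Section IX.B (Safety monitoring) opens its list with "Subjects will be withdrawn from the study at any point for the following reasons". The wording removes the patient from the study, not only from study dosing. The five reasons are:

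- "Serum IgG < 250 mg/dL at any point during the study"
- a modified BVAS-WG of 2 or more, which is the primary event
- "Require daily prednisone >7.5mg"
- WBC below 3,000
- "Serious Infections that require hospitalization"

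Other sections bear on what happens next:

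- **V.A and V.E:** BVAS/WG is scored at study visits every three months, up to a common close-out 36 months after the last enrolment. Item 4c of V.A has an investigator telephone patients who miss a visit.
- **VI.C:** intention-to-treat analysis, Kaplan-Meier estimates and a log-rank test. No censoring rule is given, and no rule for data after withdrawal.
- **VII:** a woman who becomes pregnant is removed and then followed as clinical judgment dictates.
- **IX.C:** "The following outcomes will be collected throughout the study period as appropriate".
- **End of the arm 2 description in Section I:** "Patients can be treated at any time during the study period with a total prednisone dose of ≤ 7.5 mg".

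**The concern.** Four of the five reasons can apply while BVAS/WG is below 2, so the patient leaves without the primary event and without a planned way to observe a later one. Intention-to-treat keeps that patient in the assigned arm but supplies no outcome data. Two different problems follow.

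**Steroid withdrawals may be informative.** A clinician who suspects vasculitis at a score of 0 or 1 may raise prednisone above 7.5 mg/day. That patient is withdrawn just when relapse looks likely. The trial is open-label, so the decision is unmasked and could differ by arm.

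**Safety withdrawals cost events.** The documents do not tie low IgG, low WBC or infection to flare risk, so the expected effect is lost events rather than bias. Frequencies may differ by arm. Secondary Aim 1 says "The main rituximab-associated serious adverse events noted in our cohort are infection, late-onset of neutropenia, and infusion reactions", and the arms redose on different triggers and amounts: one 1000 mg infusion on B cell return, two on an ANCA rise. Entry excludes only IgG below 300 mg/dL, so a patient can enrol 50 mg/dL above the withdrawal limit.

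**Working it through.** **Inputs from the protocol.** Section VI.D: two-sided log-rank test, alpha 0.05, relapse risks 15% and 30%, 36-month enrolment, 180 patients needed for power 0.80, 200 planned. Section V.A: close-out 36 months after the last entry.

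**Assumptions.** VI.D gives no time point for the 15%/30% risks; I take 36 months. Flare times are exponential, accrual is uniform and allocation is 1:1. Withdrawal rates are not given anywhere and are varied.

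**Reproducing the planned size.**

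- Monthly hazards: −ln(0.85)/36 = 0.00451 and −ln(0.70)/36 = 0.00991.
- HR = ln(0.85)/ln(0.70) = 0.456.
- Probability of an observed flare with entry over 36 months and close-out at 72: 1 − [exp(−36h) − exp(−72h)]/(36h), which is 0.215 and 0.411, mean 0.313.
- Freedman events: [(1.960 + 0.842)(1 + HR)/(1 − HR)]² = 56.1, rounded up to 57.
- N = 57/0.3134 = 182, against the stated 180. The plan's figure reproduces, with no visible allowance for withdrawals.
- At N = 200: 100 × 0.2155 = 21.5 and 100 × 0.4112 = 41.1 flares, 62.7 in total. Power = Φ[√62.7 × (1 − 0.456)/(1 + 0.456) − 1.960] = 84%.

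**Steroid withdrawals that remove would-be flares.** If a share f of would-be flares is withdrawn first, the observed flare hazard is h(1 − f) and the censoring hazard is hf. At N = 200:

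| Lost, lower-/higher-relapse arm | Expected flares | Observed HR | Power |
|---|---|---|---|
| none | 62.7 | 0.46 | 84% |
| 5% / 5% | 59.5 | 0.46 | 82% |
| 10% / 10% | 56.4 | 0.46 | 80% |
| 5% / 10% | 57.5 | 0.48 | 76% |
| 10% / 20% | 52.3 | 0.51 | 64% |
| 20% / 10% | 54.2 | 0.41 | 88% (effect exaggerated) |

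With no true difference (22.5% in both arms), the false-positive rate is 5% for equal loss, about 5.5% for 5% against 10%, and about 7% for 10% against 20%.

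**Safety withdrawals unrelated to flare, equal in both arms.** Add an independent hazard −ln(1 − w)/36, where w is the share withdrawn by month 36. At N = 200:

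| w | Expected flares | Power |
|---|---|---|
| 0 | 62.7 | 84% |
| 5% | 60.4 | 83% |
| 10% | 58.2 | 81% |
| 20% | 53.7 | 78% |

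The HR is unchanged throughout.

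**Sensitivity of the steroid results.** Power for no loss, 10%/10% and 10%/20%:

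| Variant | None | 10% / 10% | 10% / 20% |
|---|---|---|---|
| N = 180 | 80% | 76% | 60% |
| 15%/30% as 24-month risks | 93% | 90% | 78% |
| 15%/30% as 18-month risks | 97% | 95% | 85% |
| 48-month accrual (Section I) | 87% | 83% | 68% |

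The false-positive rate for 10% against 20% loss stays at about 7–9% in all of these.

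**Simulation check.** Log-rank tests on 10,000 simulated trials per setting, N = 200, gave power of 86% (no loss), 83% (10%/10%), 78% (5%/10%) and 66% (10%/20%). The false-positive rates were 4.9%, 4.6%, 5.2% and 7.2%. Safety withdrawal of 10% and 20% gave 83% and 81%. These agree with the formulas to within about 3 points.

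**The case against.** The strongest reply is that the demonstrable harm is small. Three of the four reasons have no shown link to flare risk, and censoring unrelated to flare does not bias a log-rank test even when it differs by arm. The 20 patients above the required 180 absorb most of the lost power: at 200, it falls below 80% only as withdrawals approach 20%. All of this stands.

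The bias route is also narrow. It needs prednisone above 7.5 mg/day, given for suspected vasculitis, at a score of 0 or 1, in a patient who would later have flared, and unequally by arm. Doses up to 7.5 mg are allowed, and a score of 2 or more already counts. The 10%/20% case means about 2 (0.10 × 21.5) against 8 (0.20 × 41.1) flares removed, and nothing in the documents suggests that rate. This stands too, and is why the figures are illustrations only.

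The reply that flares will be known anyway is weaker. Section III.B says "Subjects will be recruited from the current pool of patients in the MGH Renal and Rheumatology Units", so later flares may well come to clinical attention. But nothing commits the study to score or count them, and the missed-visit call covers patients still in follow-up. Finally, censoring is an inference, since no rule is written. It is what Kaplan-Meier and log-rank do in practice when observation stops.

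**Conclusion.** The concern holds. The withdrawal rule stops the outcome follow-up that an intention-to-treat log-rank analysis needs, and no other section restores it. For the three safety reasons the likely consequence is a loss of 1 to 6 points of power from 84% at 5–20% withdrawn, without bias. For the steroid reason, equal loss of 5–10% of would-be flares costs 2 to 4 points. Unequal loss distorts the comparison in a direction that cannot be known beforehand: it can dilute the effect (HR 0.51, power 64%) or exaggerate it (HR 0.41), and can raise the false-positive rate to about 7%. These sizes rest on assumed withdrawal shares and an assumed 36-month horizon. Small or balanced losses would do little harm. The change should be made, but the trial's validity does not hinge on it. Confidence is medium because the frequency of these withdrawals is unknown.

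**What to change.** Rewrite the withdrawal sentence in Section IX.B along these lines:

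> Prednisone >7.5 mg/day, IgG <250 mg/dL, WBC <3,000 or a hospitalized infection ends protocol-driven rituximab dosing. Unless the subject withdraws consent, scheduled BVAS/WG assessment continues to close-out, and later flares count in the randomized arm.

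Treatment after that point stays with the treating physician, as now. BVAS/WG of 2 or more remains the primary event. In addition:

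- Record a BVAS/WG score and a reason code whenever prednisone is raised above 7.5 mg/day.
- Add one log-rank analysis that also counts prednisone above 7.5 mg/day given for vasculitis activity as an event. Label it supportive, because the decision is unmasked.
- Report stops in dosing by arm and reason.

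The drafting cost is slight. The real cost is continued three-monthly visits for patients who would otherwise have left: up to about 6 years for the earliest (36 months of accrual plus 36 to close-out), though such visits were already planned for every enrolled patient. Section V.A item 4b already allows some visits by telephone with BVAS, which is a usable fallback but lacks blood work. Continued follow-up cannot recover a flare that the steroid itself prevents; the supportive analysis addresses that only in part. Removal for pregnancy (Section VII) leaves a similar but minor gap that this wording does not cover.
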